## **20.2 PRIMARY STUDY ENDPOINTS**

### **Primary Effectiveness Endpoints**

#### **MONOCULAR DISTANCE-CORRECTED INTERMEDIATE VISUAL ACUITY (DCIVA) AT 66 CM**

The first primary effectiveness endpoint for the Model ZHR00 IOL is mean (LogMAR) first-eye, monocular, distance-corrected intermediate visual acuity (66 cm) under photopic conditions at 6 months postoperative. The mean, SD, median, minimum, maximum and 95% C.I. will be reported by IOL group. Results will be reported by lens group for first eyes using one-sided, two-sample t-tests with an alpha level of 0.025. Note that a lower LogMAR value is a better acuity and a higher LogMAR value is a poorer acuity. The null hypothesis is that the mean monocular DCIVA LogMAR value for the Model ZHR00 eyes is worse than or equal to that for control eyes. The alternate

hypothesis is that the mean monocular DCIVA LogMAR value for Model ZHR00 eyes is better than that for control eyes.

$H_0: \mu_c - \mu_t \leq 0$  (Model ZHR00 lens is worse than (higher LogMAR) or equal to control)  
 $H_1: \mu_c - \mu_t > 0$  (Model ZHR00 lens is better (lower LogMAR) than control)

where

$\mu_t$  = mean LogMAR DCIVA for ZHR00

$\mu_c$  = mean LogMAR DCIVA for ZCB00

Reject the null hypothesis if one-sided p-value  $\leq 0.025$ .

The success criterion is a statistically significantly lower mean LogMAR DCIVA value for the Model ZHR00 investigational lens compared to the control lens ( $p \leq 0.025$ ). In addition, clinical significance will be determined if the median DCIVA of ZHR00 is at least 0.2 LogMAR.

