### 6.1 PRIMARY EFFECTIVENESS ENDPOINTS

#### MONOCULAR, PHOTOPIC DCIVA AT 66 CM

Success criteria:

- Statistically significant improvement in mean distance-corrected intermediate visual acuity for the ZHR00 eyes vs. control eyes
- The median DCIVA of the ZHR00 lens group is at least 0.2 LogMAR

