### 6.2 SECONDARY EFFECTIVENESS ENDPOINTS

#### MONOCULAR, PHOTOPIC DCNVA AT 40 CM

Success criteria:

- Statistically significant improvement in mean LogMAR distance-corrected near visual acuity for ZHR00 eyes vs. control eyes
- The median DCNVA of the ZHR00 lens group is at least 0.3 LogMAR

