### **Secondary Effectiveness Endpoints**

Due to multiple endpoints, a closed-form hierarchical approach will be used.

Secondary endpoints will be tested in order as follows:

---

 Rom D and B. Holland. (1995). A new closed multiple testing procedure for hierarchical families of hypotheses. Journal of Statistical Planning and Inference 46:265-275

 Rom D, R. Costello, and L. Connell. (1994). On closed test procedures for dose-response analysis. Statistics in Medicine 13:1583-1596

 Marcus R, E. Peritz, and K. Gabriel. (1976). On closed testing procedures with special reference to ordered analysis of variance. Biometrika 63:655-660.

 Huque M and A Sankoh. (1997). A reviewer's perspective on multiple endpoint issues in clinical trials. Journal of Pharmaceutical Sciences 7:545-564.

MONOCULAR DISTANCE-CORRECTED NEAR VISUAL ACUITY (DCNVA) AT 40 CM

The first secondary effectiveness endpoint is mean (LogMAR), monocular DCNVA under photopic conditions at 40 cm at 6 months. Comparisons between lens groups will be performed using a one-sided, t-test with an alpha level of 0.025. Note that a lower LogMAR value is a better acuity and a higher LogMAR value is a poorer acuity. The null hypothesis is that the mean monocular DCNVA LogMAR value for the Model ZHR00 eyes is worse than or equal to that for control eyes. The alternate hypothesis is that the mean monocular DCNVA LogMAR value for Model ZHR00 is better than that for control eyes.

$H_0: \mu_c - \mu_t \leq 0$  (ZHR00 is worse than (higher LogMAR) or equal to control)

$H_1: \mu_c - \mu_t > 0$  (ZHR00 is better (lower LogMAR) than control)

where

$\mu_t$  = the mean LogMAR DCNVA for Model ZHR00 lens

$\mu_c$  = the mean LogMAR DCNVA for control lens

Reject the null hypothesis if one-sided p-value  $\leq 0.025$ .

The success criterion is a statistically significantly lower mean LogMAR DCNVA for ZHR00 compared to ZCB00 ( $p \leq 0.025$ ). In addition, clinical significance will be determined by the median DCNVA of ZHR00 being at least 0.3 LogMAR.

OVERALL SPECTACLE INDEPENDENCE VIA BINOCULAR QUESTIONNAIRE

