## 5 POSTOPERATIVE ANALYSES – PRIMARY AND SECONDARY EFFECTIVENESS ENDPOINTS

### 5.1 PRIMARY EFFECTIVENESS ENDPOINTS

#### 5.1.1 MONOCULAR DISTANCE CORRECTED INTERMEDIATE VISUAL ACUITY (DCIVA)

The first primary effectiveness endpoint is mean (logMAR) first-eye, monocular, distance corrected intermediate visual acuity (66 cm) at 6 months postoperative. Results will be reported by lens group for first eyes using one-sided, two-sample t-tests with alpha level of 0.025. Note that a lower LogMAR value is a better acuity and a higher LogMAR value is a poorer acuity. The null hypothesis is that the mean LogMAR value for ZHR00 eyes is worse than or equal to that for control eyes. The alternative hypothesis is that the mean for ZHR00 eyes is better than that for control eyes.

$H_0: \mu_c - \mu_t \leq 0$  (ZHR00 is worse than (higher logMAR) or equal to control)

$H_1: \mu_c - \mu_t > 0$  (ZHR00 is better (lower logMAR) than control)

where

$\mu_t$  =mean LogMAR DCIVA for ZHR00

$\mu_c$ = mean LogMAR DCIVA for ZCB00

Reject the null hypothesis if one-sided p-value  $\leq 0.025$ .

The success criterion is a statistically significantly lower mean LogMAR DCIVA score for ZHR00 compared to ZCB00 ( $p \leq 0.025$ ). In addition, clinical significance will be determined by:

- The median DCIVA of the ZHR00 first eyes is at least 0.2 LogMAR.

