## 5.2 SECONDARY EFFECTIVENESS ENDPOINTS

### 5.2.1 MONOCULAR DISTANCE CORRECTED NEAR VISUAL ACUITY (DCNVA)

The first secondary endpoint is mean (LogMAR) first-eye, monocular, distance corrected near visual acuity under photopic conditions at 40 cm at 6 months postoperative. Results will be compared between lens groups for first eyes using one-sided, two-sample t-tests with alpha level of 0.025. The null hypothesis is that the mean LogMAR value for ZHR00 eyes is worse than or equal to that for control eyes. The alternative hypothesis is that the mean for ZHR00 eyes is better than that for control eyes.

$H_0: \mu_c - \mu_t \leq 0$  (ZHR00 is worse than (higher LogMAR) or equal to control)

$H_1: \mu_c - \mu_t > 0$  (ZHR00 is better (lower LogMAR) than control)

where

$\mu_t$  =mean DCNVA LogMAR for ZHR00

$\mu_c$  = mean DCNVA LogMAR for ZCB00

Reject the null hypothesis if one-sided p-value  $\leq 0.025$ .

The success criterion is a statistically significantly lower mean LogMAR value for ZHR00 compared to ZCB00 ( $p \leq 0.025$ ). In addition, clinical significance will be determined by:

- The median DCNVA of ZHR00 first eyes is at least 0.3 LogMAR

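### The median DCIVA and DCNVA success criteria are written as LogMAR minimums although lower LogMAR is better, so taken numerically they are reversed

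*Protocol*

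**What the plan says.** Both endpoints have a two-part success definition: a one-sided t-test showing a lower mean LogMAR for ZHR00, and a clinical criterion on the ZHR00 median. The clinical criterion appears in six places.

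DCIVA at 66 cm (primary):
- Protocol 6.1: "The median DCIVA of the ZHR00 lens group is at least 0.2 LogMAR"
- Protocol 20.2: "clinical significance will be determined if the median DCIVA of ZHR00 is at least 0.2 LogMAR"
- SAP 5.1.1: "The median DCIVA of the ZHR00 first eyes is at least 0.2 LogMAR"

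DCNVA at 40 cm (first secondary):
- Protocol 6.2: "The median DCNVA of the ZHR00 lens group is at least 0.3 LogMAR"
- Protocol 20.2: "clinical significance will be determined by the median DCNVA of ZHR00 being at least 0.3 LogMAR"
- SAP 5.2.1: "The median DCNVA of ZHR00 first eyes is at least 0.3 LogMAR"

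None of the six adds a direction, a Snellen equivalent or an inequality sign. The synopsis lists the endpoints without the median criterion, so it does not settle the point.

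The direction of the scale is given elsewhere. Protocol 20.2 states under DCIVA: "Note that a lower LogMAR value is a better acuity and a higher LogMAR value is a poorer acuity". The same note appears under DCNVA in Protocol 20.2 and in SAP 5.1.1. SAP 5.2.1 gives the direction through its alternative hypothesis: "ZHR00 is better (lower LogMAR) than control".

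**The concern.** The two halves of one success definition point in opposite directions if each is taken at face value. The t-test requires a lower LogMAR for ZHR00, while the clinical criterion requires the ZHR00 median to reach or exceed a LogMAR value, that is, to be no better than the threshold.

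The literal reading is not contrived. The other success criteria use the same phrase as an ordinary ≥: the 0.5 D gain in depth of focus and the 25-percentage-point gain in spectacle independence. A programmer who coded the phrase the same way throughout would code the reversed rule.

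Protocol 20.1 and SAP 2.1 place the clinical criterion in the safety population and say that it involves no inferential comparison. It is one number set against a threshold, so the wording decides pass or fail. If the direction is clarified only after results are known, it will look like a post hoc reinterpretation of a prespecified criterion.

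**Working it through.** **The plan's own figure.** Protocol 20.7 and SAP 7.1 and 7.2 claim over 90% power for a 1-line difference, with SD 1.6 lines, one-sided alpha 0.025 and 100 per group.
- Standardised difference: 1 / (1.6 × √(2/100)) = 1 / 0.2263 = 4.42.
- Power: Φ(4.42 − 1.96) = Φ(2.46) = 0.993. The noncentral t with 198 df also gives 0.993.

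The claim reproduces, and the median criterion plays no part in it.

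**Conversions (SAP Appendix II).**
- Intermediate: LogMAR = (85 − letters)/50
- Near: LogMAR = (70 − letters)/50
- Snellen denominator = 20 × 10^LogMAR

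**Thresholds in other units.**
- DCIVA 0.2: 85 − 50 × 0.2 = 75 letters; 20 × 10^0.2 = 31.7, about 20/32.
- DCNVA 0.3: 70 − 50 × 0.3 = 55 letters; 20 × 10^0.3 = 39.9, about 20/40.

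More letters give a lower LogMAR. Read numerically, the criteria therefore ask for a median of 75 letters *or fewer* at 66 cm and 55 letters *or fewer* at 40 cm.

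**Two example medians under both readings.**

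| ZHR00 median | Letters at 66 cm / 40 cm | Snellen | Read as ≥ 0.2 / ≥ 0.3 | Read as ≤ 0.2 / ≤ 0.3 |
|---|---|---|---|---|
| 0.10 | 80 / 65 | 20/25.2 | fails / fails | meets / meets |
| 0.35 | 67.5 / 52.5 | 20/44.8 | meets / meets | fails / fails |

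(A half-letter median can arise as the midpoint of two scores.) The two readings agree only when the median equals the threshold exactly.

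**How sharply the readings separate.** I simulated 100 eyes with SD 0.16 LogMAR (1.6 lines × 0.1), assumed normal and rounded to single letters (0.02), with 20,000 replicates. The documents give no expected median, so the true values below are assumptions.

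| Assumed true DCIVA median | Meets criterion, ≥ 0.2 | Meets criterion, ≤ 0.2 |
|---|---|---|
| 0.10 | 0% | 100% |
| 0.15 | 1.9% | 99.8% |
| 0.20 | 65% | 65% |
| 0.25 | 99.9% | 1.7% |
| 0.30 | 100% | 0% |

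Both columns exceed 50% at 0.20 because a median exactly at the threshold passes either way. DCNVA shows the same pattern around 0.3.

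**The case against.** The strongest reply is that no careful reader would apply the reversed rule. The sentence concerns a level of acuity, and a level of at least 0.2 LogMAR can be understood as that acuity or better. The surrounding text supports this:
- The scale direction is stated in the same section, or is visible in the hypotheses.
- The paired statistical criterion asks for a lower mean.
- The defocus endpoint (Protocol 20.2, SAP 5.1.2) uses the same 0.2 threshold with its direction spelled out.
- Note 2 to Table 1 in Protocol 7.1 speaks of acuity above 0.2 LogMAR and means better acuity.

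On this view the point is editorial.

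The inference about intent stands, and I do not suggest that the sponsor meant the reversed rule. It is still an inference drawn against the numeric meaning of the phrase, and a pass/fail rule for a primary endpoint should not need one. The context does not exclude the literal rule either: a ZHR00 median worse than 0.2 can coexist with a significantly lower mean than control if the control mean is higher still.

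Two further points are fair. The pass rates above show what happens if the literal rule is applied, not that anyone would apply it. The reach is also limited: SAP 2.5 lets testing proceed down the hierarchy on statistical significance alone, even when a clinical criterion is not met.

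**Conclusion.** The concern holds. The clinical success criteria for a primary endpoint and for the first secondary endpoint give the wrong pass/fail result if followed numerically, in all six places where they are stated. The reversal is deterministic. It follows from the direction of the scale and the SAP's conversion formulas and does not depend on the simulation, whose assumed medians, normality and SD only illustrate it.

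The consequence is confined to whether the clinical half of these two endpoints is declared met. It should be corrected, but it does not threaten the inferential analysis.

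**What to change.** In Protocol 6.1, Protocol 20.2 (DCIVA) and SAP 5.1.1, write *median DCIVA of 0.2 LogMAR or better (median ≤ 0.2)*. In Protocol 6.2, Protocol 20.2 (DCNVA) and SAP 5.2.1, write *median DCNVA of 0.3 LogMAR or better (median ≤ 0.3)*. This keeps the sponsor's thresholds and follows the form already used for the defocus endpoint. Make the change before unmasking.

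The cost is one phrase in each place, with no effect on data collection, tests or sample size. Four of the six edits are to the protocol, and Protocol 12 requires FDA and IRB approval for modifications; whether that reaches a sponsor's wording correction is arguable. If it causes delay, correct the two SAP sections first, since they govern the analysis, and align the protocol at its next amendment.

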### MONOCULAR DISTANCE-CORRECTED DEFOCUS

The second primary effectiveness endpoint is monocular mean diopters of defocus where visual acuity is LogMAR 0.2 or better at 6 months postoperative. The diopters of defocus where the mean visual acuity of LogMAR 0.2 or better is achieved will be derived by visual inspection of the defocus curve. The defocus endpoint will only be determined from zero to the negative powers; however, the mean of each diopter will be plotted for the range the testing conducted (including positive and negative diopters).

The success criterion is that the Model ZHR00 lens will demonstrate at least 0.5 D greater monocular, photopic, distance-corrected depth of focus compared to the control IOL at 0.2 LogMAR visual acuity threshold, based upon visual inspection of the defocus curves.

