#### MONOCULAR, DISTANCE-CORRECTED DEFOCUS CURVE

Success criteria: The Model ZHR00 lens demonstrates at least 0.5 D greater monocular, photopic, distance-corrected depth of focus compared to the control IOL at 0.2 LogMAR visual acuity threshold, based on visual inspection of the defocus curves.

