#### DEFOCUS TESTING (MASKED PROCEDURE)

Monocular and binocular best-corrected distance defocus testing will be performed on all subjects at the 6-month visit in accordance with the methodology described in the draft standard for Extended Depth of Focus Intraocular Lenses from the American National Standards Institute (ANSI Z80.35 v7). While the testing includes plus-power defocus, the study endpoint is based upon minus-power defocus results.

Defocus testing will be performed under photopic conditions (85 cd/m^2, 80-110 cd/m^2 acceptable) using the M&S System at 4.0 meters with the ETDRS refraction in place (no adjustment necessary for test distance). The subject is to be defocused in -0.50 D increments from +2.00 D through +4.00 D. Defocusing can be done with either spherical loose trial lenses or plus- and minus-power lens racks.

At each defocus increment, a LogMAR visual acuity is to be obtained and recorded. Further instructions for defocus testing are detailed in **Appendix I**.

The following defocus curve measurements are to be performed per the visit schedule in **Appendix A**:

Test	Test Distance	Illumination	Type of Testing	Refraction Adjustment
Defocus	4 m	Photopic (85 cd/m  )	Monocular, first eye only Binocular	No adjustment; ETDRS Rx only

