### 20.1 ANALYSIS POPULATION

The primary analysis population for the primary DCIVA and secondary DCNVA endpoints will be a modified Intent-to-Treat (mITT) analysis for all first-eyes randomized and implanted with either a test or control study IOL. Sensitivity analyses using all randomized subjects will be performed as described below. The validation work for the PRSIQv2 was based on a complete data set (i.e., with non-missing values) for each composite dichotomous score and recommended that imputations for missing values not be used. Therefore, the primary analysis population for overall spectacle independence will be the safety population (SP) with subjects who are bilaterally implanted with the same study lens in both eyes. For all subjects with missing data for the spectacle independence endpoint at the 6-month visit, information (e.g., percentage missing, reason for missing data, etc.) will be provided. There are no inferential statistics for the defocus curve primary endpoint; therefore safety population (SP) will be the primary analysis population for this endpoint. The mITT population will be used for the statistical success criterion of the primary DCIVA endpoint and secondary DCNVA effectiveness endpoint where SP will be used for the clinical success criterion of those endpoints since there is no inferential statistics comparison for the clinical success criterion.

For eyes that do not have data available at the 6-month postoperative visit, other than PRSIQv2, data will be imputed for the mITT analyses. For continuous variables (DCIVA and DCNVA), planned method to use is the MCMC full-data imputation as described in Little & Rubin. Data imputation and analysis will be performed using the MI and MIANALYZE procedures in SAS® (Version 9.4).

In addition to the above imputation methods, sensitivity analyses using different imputation approaches (worst-case scenario, best-case scenario and tipping point) will also be performed for primary DCIVA and secondary DCNVA and safety endpoint of mean BCDVA. These analyses will be performed using all randomized subjects with the IOL group based on the randomization. A worst-case scenario (with the worst score assigned to missing data) for the test IOL and the best score assigned to missing data for the control IOL will be performed. A best-case scenario will also be performed (assigning the best value to missing test IOL data and the worst value to missing control

---

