## APPENDIX I INSTRUCTIONS FOR DEFOCUS TESTING

All defocus testing is to be performed in accordance with the methodology described in the draft ANSI Z80.35 Extended Depth of Focus draft standard (v7), under photopic conditions using the M&S System at a test distance of 4.0 meters, a trial frame, and loose trial lenses or retinoscopy lens racks. Subjects should be reminded prior to testing that squinting is not allowed and the testing technician should carefully observe to ensure the subject is not squinting. If squinting is observed, the subject is to be reminded by the testing technician not to squint.

This test is to be done at the 6-month visit for all subjects.

Monocular Defocus Testing (First eye only): With the subject's distance correction in place for the first eye and the second eye occluded, defocus the image by +2.00 D over the manifest distance correction in the first eye, using a plus-power loose trial lens or a retinoscopy lens rack. Start the test by instructing the subject to read as many letters as possible on the M&S system, even if the subject must guess. The technician will control movement through charts based on subject responses and the system will end the testing when a threshold is reached. The number of letters correctly read and the LogMAR score will be displayed on the laptop screen; record the total number of letters correct in EDC. Continue to change the defocus in -0.50 D increments using loose trial lenses or the retinoscopy lens rack, repeating the test and recording the total number of letters correct at each level of defocus up to -4.00 D over the subject's manifest distance correction.

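### The second primary endpoint (0.5 D more depth of focus than control) is read by eye from mean curves tested every 0.50 D, with no stated reading rule, so near the margin the verdict can depend on how the curve is read

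*Protocol*

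**What the plan says.** Protocol Section 6.1 sets success as at least 0.5 D more monocular, photopic, distance-corrected depth of focus than the control lens "at 0.2 LogMAR visual acuity threshold, based on visual inspection of the defocus curves". Section 20.2 says how the value is obtained: the defocus level at which "mean visual acuity of LogMAR 0.2 or better is achieved will be derived by visual inspection of the defocus curve". Only the range from zero to minus powers counts. SAP Section 5.1.2 repeats both statements.

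On step size, Protocol Appendix I instructs: "Continue to change the defocus in -0.50 D increments using loose trial lenses or the retinoscopy lens rack". The success margin therefore equals one test step.

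On inference, Protocol Section 20.1 states: "There are no inferential statistics for the defocus curve primary endpoint". SAP Section 2.1 agrees. No interval or test accompanies the reading.

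On external method, Protocol Section 10.7 has defocus testing done "in accordance with the methodology described in the draft standard for Extended Depth of Focus Intraocular Lenses", and Appendix I does the same. SAP Section 7 cites that draft for sample size. Neither document reproduces a rule from it for deriving depth of focus. SAP Appendix II gives formulas for acuity, refraction and contrast sensitivity, but none for this quantity.

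**The concern.** The text supports two readings. The phrase in Section 20.2 about acuity of 0.2 or better being achieved fits the last tested step whose mean is at or below 0.2 LogMAR. The threshold phrase in Section 6.1 fits the point where the plotted curve crosses 0.2. Because the margin is exactly one step, a last-step reading can turn a small gain into a full 0.5 D.

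This is one of two primary effectiveness endpoints, and the reading alone decides it. If the rule is not fixed beforehand, it could be settled after the group curves have been seen, and an observed gain well below the plan's own criterion could be declared a success.

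**Working it through.** **The plan's own figures.** Neither document gives power or precision for the defocus endpoint. The nearest figure is for DCIVA: over 90% power for 1 line, SD 1.6 lines, 100 per group, one-sided 0.025. The standard error is 1.6 × √(2/100) = 0.226 lines, 1/0.226 = 4.42, and Φ(4.42 − 1.96) = 99.3%. That reproduces, but it says nothing about depth of focus.

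**Worked example (illustrative means, LogMAR).**

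| Defocus | ZCB00 | ZHR00 |
|---|---|---|
| −1.0 D | 0.11 | below 0.20 |
| −1.5 D | 0.21 | 0.19 |
| −2.0 D | above 0.20 | 0.31 |

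- Last tested step at or below 0.20: control 1.0 D, ZHR00 1.5 D, gain 0.5 D, pass.
- Linear interpolation: control 1.0 + 0.5 × (0.20 − 0.11)/(0.21 − 0.11) = 1.45 D; ZHR00 1.5 + 0.5 × (0.20 − 0.19)/(0.31 − 0.19) = 1.54 D; gain 0.09 D, fail.

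**Direction of error under fixed rounding.** Suppose both crossings are read to a unit u that divides 0.5 D. Adding 0.5 D to a crossing then adds exactly 0.5 D to its reading, so a gain of 0.5 D or more always passes. With the control crossing spread evenly over a unit, a smaller gain g passes with probability 1 − (0.5 − g)/u for 0.5 − u < g < 0.5. At g = 0.40 this is 0.80 for u = 0.5 (last step), 0.60 for u = 0.25 and 0 for u = 0.1. These readings err only toward success.

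**Direction of error under free reading.** Suppose each crossing is read with independent error of SD 0.05 D (assumed). The read gain then has error SD 0.05 × √2 = 0.071 D. An observed gain of 0.55 D reads below 0.5 D with probability Φ(−0.05/0.071) = 24%; with SD 0.03 or 0.10 D this is 12% or 36%. Rounding to 0.2 D, which does not divide 0.5, fails an exact 0.50 D gain for 40% of control crossings between 1.0 and 1.5 D. Free reading can err either way.

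**With sampling error (simulation).** Assumed inputs: SD 0.16 LogMAR per point (borrowed from the DCIVA calculation), 100 eyes per arm, straight-line means with slope 0.20 LogMAR per D, within-eye correlation 0.8, control crossing uniform on 1.0 to 1.5 D. The documents give no defocus SD, slope, correlation or control crossing. Chance of declared success:

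| True gain | Last step | Read to 0.25 D | Read to 0.1 D | Linear interpolation |
|---|---|---|---|---|
| 0.25 D | 50% | 17% | 4% | 1% |
| 0.40 D | 78% | 57% | 33% | 18% |
| 0.50 D | 91% | 83% | 67% | 50% |
| 0.60 D | 98% | 96% | 91% | 82% |

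For a true 0.40 D gain, over slopes 0.10 to 0.30 and correlations 0.5 and 0.8, last step passes 71–79% and interpolation 7–32%.

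**If the drawn curve's crossing is read exactly.** Linear and cubic-spline readings were compared on curved means at true gains of 0.40 to 0.60 D. The gains differ by 0.007 to 0.015 D on average, and the verdicts differ in 1.2–5.6% of simulated trials. At a true 0.50 D gain, linear passed while the spline failed in 1.3–2.3% of trials, and the reverse occurred in 0.5–0.7%.

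**The case against.** **The crossing is the more natural reading.** Inspecting a plotted curve at a threshold suggests reading where it crosses; a last-step value could come from a table of means. This has force, and if the crossing is meant and read exactly, little ambiguity remains. But the other phrase permits the last-step reading, and no text chooses between them. The 0.25 and 0.1 D reading units are illustrations and appear in neither document.

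**The true gain may be far above the margin.** The version 2.0 change-history entry on defocus increments places the intended extension of focus between −2.0 and −4.0 D. Section 7.1 says the optic is meant to extend focus beyond the parent lens, and Table 1 lists a range of vision through 3.0 D. If the control crosses at 1.0 to 1.5 D (assumed) and ZHR00 at 2.0 D or beyond, the gain is at least 0.5 D and last step and interpolation agree. These are design intentions: Table 1 states no basis for the 3.0 D, and the parent's 2.0 D is binocular. They still make a near-margin result less likely, which limits the practical weight of the point.

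**The cited draft standard may contain a rule.** It may; it cannot be checked here. It is cited for testing and sample size, not for deriving this endpoint.

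**Stronger readings to avoid.** A reader might infer that reading by eye can only favour the test lens, or that a gain of 0.5 D or more passes however it is read. Neither follows: the one-way result belongs to last-step reading and to rounding in units that divide 0.5 D. A reader might also take the acuity criteria as evidence that a near-margin result is expected. Those criteria are "The median DCIVA of the ZHR00 lens group is at least 0.2 LogMAR" at 66 cm (1/0.66 = 1.52 D) and "The median DCNVA of the ZHR00 lens group is at least 0.3 LogMAR" at 40 cm (2.50 D). Reading them as 0.2 or better and 0.3 or better, and treating medians as means, a lens just meeting both has slope 0.10/0.985 = 0.1015 and a mean of 0.20 − 0.1015 × 0.015 = 0.1985 at −1.5 D. That places only the ZHR00 curve. The gain also needs the control crossing, which the plan does not give. Assuming 1.3 D with control slopes of 0.20 to 0.30 implies a DCIVA difference of about 0.043 to 0.065 LogMAR, short of the 0.10 the plan is powered for.

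**Conclusion.** The concern holds in a limited form. A primary endpoint is decided by eye, the margin equals the test step, and the wording allows two readings that can give opposite verdicts near 0.5 D. The worked example shows this by arithmetic alone. The size of the effect, about 78% against 18% declared success at a true 0.40 D gain, rests entirely on the assumed SD, slope, correlation and control crossing. The documents do not show that the method is biased in one direction or that a near-margin result is expected. The point should be fixed because the remedy is cheap and a primary verdict should not depend on an unstated reading.

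**What to change.** In Protocol Sections 6.1 and 20.2 and SAP Section 5.1.2, replace visual inspection with a programmed value. Define depth of focus as the distance from 0 D to the first minus-side crossing of 0.20 LogMAR on the group-mean curve, by linear interpolation between adjacent tested points, set to 4.0 D if the curve never crosses. Success is a ZHR00 minus ZCB00 difference of at least 0.50 D. If the cited draft ANSI standard already fixes a reading rule, write that rule into both documents instead.

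Report a bootstrap 95% confidence interval, resampling eyes within arm, as descriptive only. Point SAP Section 6.2, which applies the same method to the binocular curve, to this definition. Linear interpolation is itself a choice, so fix it before unmasking.

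Two clerical items can go in the same amendment. Section 10.7 gives the range as "The subject is to be defocused in -0.50 D increments from +2.00 D through +4.00 D", while Appendix I and SAP Section 5.1.2 end at −4.0 D; these must be reconciled. The endpoint is also introduced as mean diopters, which can be read as an average of per-eye depths, and should be matched to the mean-curve definition.

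The cost is a protocol and SAP amendment with the FDA and IRB approvals required by Protocol Section 12, and a few lines of code, with no new data or visits. The downside is a lower chance of success near the margin than a last-step reading would give: under the simulation assumptions, about 50% against 91% at a true 0.50 D gain, and 82% against 98% at 0.60 D.
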